Statistical Analysis. An overview the statistical analysis used for each aim is presented in this section. Recent advances in statistical modeling have resulted in the specification of multilevel models that can provide effect sizes for each treatment element while also accounting for the specific features of single-case experimental designs (e.g., handling auto-correlation among consecutive datapoints, correcting for design-specific error structures). These advances have resulted in statistical packages in the R statistics platform (e.g., *sdhlm*). These tools were used to analyze results for Aims 1, 3, and 4. Specific model parameters are presented in the Results section.

Multilevel modeling for Aim 1: Effects of the group consultation model and each consultation component on clinician manual adherence and parent coaching competency. Only data from the 3 agencies with sufficient baseline data were used for Aim 1 analysis. We examined the effects of individual components of the group consultation model (i.e., consultation training activities) on clinician fidelity (i.e., manual adherence, parent coaching competency). To do so, we utilized 2-level multilevel models to estimate the change in level from the average baseline fidelity score to the average fidelity level for each consultation training activity condition (i.e., changes in level from baseline to each consultation condition). For example, the model estimated the magnitude of change from the Baseline level to the Feedback level, and whether the change was statistically significant. Specific model parameters for all models are presented in the Results section.

The models provide two sets of estimates: 1) the average effect of each consultation component on fidelity scores *averaged across clinicians* (i.e., results from the 2-level model),

and 2) *participant-specific* parameter estimates that demonstrate the effect of consultation components on an individual clinician's fidelity scores. First, estimates for the 2-level model (averaging across clinicians) include estimated fixed effects for each consultation component and random deviations for each clinician. These deviations are obtained from the random effect estimates, which included an intercept for each clinician and a random component for each of the 3 consultation phases. These random effects for the intercept allow the model to vary for each clinician in regard to their baseline fidelity level. The random effects for each consultation component allowed for the estimated effects of each consultation component to vary across clinicians (e.g., the effect of feedback could have a stronger magnitude for clinician 0201 than 0502). Next, the participant-specific parameters are estimated using the fixed and random effect estimates from the 2-level model. They are a combination of fixed effects and the between-participant variance. These participant-specific parameters quantify the effects of each consultation component on an individual clinician's fidelity levels. However, the model does not compute tests of statistical significance for effects of each consultation component on individual clinicians. In order to test whether the observed effects were statistically significant for a given clinician, one would need to fit separate multilevel models for each of the 5 outcome variables for each clinician (a total of 60 separate models), which was beyond the scope of this project. Also, those separate individual multilevel models would not account for between-participant variation, which is a major strength of the two-level multilevel models used in this analysis. Although we hoped to include a third level of nesting (i.e., agency-level effects such as how the rurality of agency #1 affects estimates), our sample size was too small to do so.

Aim 2: Relative usability of each consultation component. We examined statistical differences among mean ratings of each consultation component (i.e., training activity) on the

Implementation Strategy Usability Scale. Usability ratings were averaged for each consultation condition for each clinician and then examined using a repeated measures one-way ANOVA. Questionnaires from all 6 agencies were utilized for this analysis.

Aim 3: Effects of the group consultation model on case penetration and clinician perceptions of Project ImPACT over time. We used two-level multilevel models to examine changes in case penetration and clinician perceptions of Project ImPACT from the Baseline phase to the Consultation phase. Observations (i.e., weekly case penetration data, overall PCIS scores) were nested within clinicians. Questionnaires from all 6 agencies were utilized for this analysis. We ran separate case penetration models for clients using Medicaid insurance and clients using private insurance/self pay.

Due to the fairly homogenous small sample size and concerns about including too many predictors in the model, we did not include clinician demographics/previous training experiences in the multilevel model predicting perceptions of Project ImPACT on the PCIS. However, we were still interested in the relationship between these variables and PCIS scores. Thus, we examined the relationships between PCIS scores averaged for each clinician and a number of provider demographic, training, and caseload variables using Pearson's correlations for interval data and Spearman's rho for ordinal data.

Exploratory Aim 4: Effect of Project ImPACT on child social communication outcomes over time. We fit a series of two-level multilevel models to estimate the extent to which Project ImPACT was associated with changes in parent-reported child social communication outcomes over time. Observations (i.e., caregiver ratings on the Autism Impact Measure) were nested within each child. There were 3 multilevel models in total (Communication, Social Reciprocity,

and Peer Interaction). Questionnaires from families across 5 agencies with sufficient data were utilized for this analysis.

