Design overview. Groups of 3-5 clinicians were recruited by each agency leader. Once all clinicians at an agency were enrolled, they had a 2-week initial training period in which they completed the Project ImPACT Beginner e-Course, a 6-hour self-directed online tutorial on Project ImPACT intervention content. The Beginner e-Course consisted of didactic modules with slides and audio recordings about Project ImPACT NDBI intervention strategies and best practices for collaborating with parents. Modules included video examples of caregivers implementing the intervention strategies and periodic quizzes about course content, but did not include explicit instruction about parent coaching.

Following the initial training period, clinicians entered the Baseline Phase (3 to 9 weeks; randomized by agency) during which they were asked to follow the Project ImPACT coaching manual and meet weekly with their enrolled families, but did not receive consultation support. After the baseline phase, all enrolled clinicians at each agency entered the consultation phase, during which they received 12 group consultation sessions, once per week, for 1.5 hours per session. The consultation phase included three, 4-week blocks in which the group completed one consultation training activity per block (i.e., case support, skill rehearsal, or feedback on

videotaped sessions). Clinicians submitted recordings of all Project ImPACT telehealth sessions throughout the Baseline and Consultation phases, and then again at Follow Up (8-weeks post consultation). Information about the procedures used in each phase is outlined below.

Baseline phase. Clinicians received an e-book copy of the Project ImPACT Coaching Manual, which includes detailed descriptions about the theoretical underpinnings of the intervention and lesson plans for each of the 24 sessions (e.g., session agendas, handouts, access to video models of NDBI intervention strategies, examples of trouble-shooting tips for common challenges with clients). Clinicians also received an e-book copy of the Project ImPACT Parent Manual, which includes descriptions of the NDBI strategies in parent-friendly language and tips about how to apply NDBI strategies at home and in the community. Clinicians were instructed to follow the lesson plans in the Project ImPACT coach manual and no consultation support was provided during the Baseline phase.

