Baseline lengths were randomized by a statistician unaware of agency characteristics using a random-number generator. Published standards for single-case designs require a minimum of 3 observations per phase to “meet standards with reservations” (Kratochwill et al., 2013). See Table 2 for the baseline lengths for each agency. Baseline lengths for agencies 1-4 were randomized for 3-6 weeks. Due to a methodological challenge (outlined below), baseline lengths for agencies #5 and #6 were randomized for 6-9 weeks to ensure that clinicians had sufficient baselines.

Consultation phase. Group consultation sessions took place via a teleconference platform (Zoom). During a given consultation condition (i.e., 4-week block in which only one consultation training activity was delivered), no components of any other conditions were provided. For example, during the skill rehearsal condition, no feedback was given about the role

plays, so that the only performance feedback clinicians received occurred in the feedback condition. All providers received each of the 3 consultation conditions (i.e., training activities), with each training activity delivered in isolation for a given 4-week consultation period. The order in which providers received each component was randomized for each agency by a statistician unaware of agency characteristics using a random-number generator, such that each agency had an equal chance of receiving one of the predetermined permutations of conditions (e.g., equally as likely to be randomized to ABCD order as ADCB order). Consultation sessions were rescheduled for the following week if more than half of participants at an agency would not be present or if the consultant would not be present. See Table 2 for the consultation component order for each agency.

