Methodological challenge with the baseline phase. The research team became aware of a methodological flaw following visual analysis of manual adherence data from the first 4 agencies. Within-condition visual analysis indicated that baselines across agencies were unstable due to inflation of the manual adherence scores for the first 2 sessions of Project ImPACT, as compared to sessions 3-24. Conceptually, this made sense because these 2 sessions were atypical and did not include instruction on NDBI techniques nor an active parent coaching component in which clinicians provided feedback; session 1 was an overview of the program and session 2 was a goal setting session. Both sessions are much less complex than the other parent coaching sessions. Agencies #1-4 had started data collection by this point, and due to the initial randomization procedure using parameters of 3-6 weeks of baseline, only 1 agency had at least 3 weeks of usable baseline sessions (Agency #2). For this reason, an additional 2 agencies were recruited (Agencies #5 and #6), and baseline lengths for those agencies were randomized for 6-9 weeks to ensure that baseline lengths had at least 3 usable Project ImPACT sessions. Additionally, to allow for the retention of all clinicians in Agencies #5 and #6, baselines for those two agencies were extended by 1 week to allow for clinicians who had multiple cancellations in the baseline period to acquire at least 2 usable baseline sessions.

Consultant Fidelity to Consultation Conditions

Consultant fidelity to the three consultation conditions was assessed by 2 coders naïve to condition and timepoint using the Project ImPACT Consultation Adherence Checklist. The checklist included scores for the percentage of required training activities for each of the 3 consultation components, as well as the length of time spent on the training activities (e.g., time

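### Component order is described as drawn separately for each agency with no counterbalancing across agencies, so block-position balance in the three Aim 1 agencies was left to chance

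*Combined protocol and SAP*

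**What the plan says.** The Design overview sets out "three, 4-week blocks in which the group completed one consultation training activity per block". On order, the Consultation phase section states: "The order in which providers received each component was randomized for each agency by a statistician unaware of agency characteristics using a random-number generator". It adds that "each agency had an equal chance of receiving one of the predetermined permutations of conditions", with the example "equally as likely to be randomized to ABCD order as ADCB order". The section does not list the permutations, say whether an order could be drawn twice, or mention any constraint linking one agency's order to another's. It sends the reader to Table 2 for the realised orders.

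For the analysis set, Multilevel modeling for Aim 1 says: "Only data from the 3 agencies with sufficient baseline data were used for Aim 1 analysis". The section on the methodological challenge with the baseline phase reports that, of agencies #1 to #4, only #2 had at least three weeks of usable baseline, and that #5 and #6 were recruited for this reason. The Aim 1 trio is therefore inferred to be #2, #5 and #6.

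The Aim 1 model is described as fixed effects for each component against baseline, with clinician random effects for the intercept and for each component. Specific parameters are deferred to the Results. Aim 2 is a one-way repeated-measures ANOVA on usability ratings from all six agencies.

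**The concern.** Specific Aim 1 predicts that Feedback raises fidelity beyond what the other two components achieve, and the design is said to support causal interpretation of treatment elements. That is a comparison between components, each given once per agency in one of three consecutive blocks. The components are training. If skills gained in block 1 persist, whatever comes third is compared with baseline after two earlier rounds of training. A component that tends to fall late would be credited with accumulated gains, or with any drift over the 12 weeks.

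The protection against this is variation of order across agencies. The visual analysis section explains that there is no replication within an agency, and it sets time effects aside only within a four-week block, not across blocks. Its rule that an effect must appear in all three agencies does not help if a component holds the same position in all three, because the position effect would be replicated with it. The Aim 2 ANOVA likewise names no position factor.

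**Working it through.** **Inputs.** Three components and three block positions (Design overview). One order per agency, equal chances (Consultation phase). Three agencies in Aim 1 (Multilevel modeling for Aim 1). Assumption: the predetermined permutations are all 3! = 6 orders. The plan gives no probability of balance, so there is no figure to reproduce.

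**Perfect position balance in three agencies.** This requires a 3×3 Latin square. There are 2 such squares of three components and 3! ways to assign the rows to agencies: 2 × 6 = 12 favourable outcomes.
- Independent draws: 12/6³ = 12/216 = 5.6%.
- No repeats: 12/(6×5×4) = 12/120 = 10.0%. The result is also 10.0% for #2, #5 and #6 if six agencies share the six orders.
- #5 and #6 drawn without repeats from a fresh set: 12/(6×6×5) = 12/180 = 6.7%.

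**Feedback in three different positions.**
- Independent: 3!/3³ = 6/27 = 22%.
- No repeats: (6×4×2)/120 = 48/120 = 40%.

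**Some component in the same position in all three agencies.**
- Independent: for one named component, 3 × (1/3)³ = 1/9 = 11%. If two components hold fixed positions so does the third, which means that all three orders are identical: 6/216 = 1/36. By inclusion–exclusion, 3(1/9) − 3(1/36) + 1/36 = 10/36 = 60/216 = 27.8%.
- No repeats: a given component holds a given position in only 2 of the 6 orders, so three distinct orders cannot share it. Probability 0.

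**What this does to the contrasts.** Component contrasts were checked for estimability after adjusting for agency and block position, over every possible triple.
- Independent draws: all three contrasts are estimable in 156/216 = 72%. In 60 − 6 = 54 triples (25%), one component is tied to one position and only the contrast between the other two survives. In 6/216 = 2.8%, none survives.
- No repeats: all contrasts are estimable in 120/120.

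**Sensitivity to the unstated set.** The two example orders both put C in the middle block, so no three-order Latin square contains both. The only position-balanced set of distinct orders containing both is the full six. Sets of two or three orders containing both examples give 0% balance. Sets of four give 0 to 9.4% with repeats and 0 to 25% without. Sets of five give 4.8% and 10%. If agencies #1–3 and #4–6 had each been given a Latin square, #2, #5 and #6 would be balanced with probability 0% (opposite squares) or 33% (same square).

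**Predecessors.** With the six orders used once each, every component comes first twice and follows each of the other two twice. In a single Latin square such as BCD, CDB, DBC, C only ever follows B, D only C, and B only D.

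**The case against.** The case against has real force. Silence about counterbalancing does not prove that there was none: equal marginal chances are compatible with a restricted scheme, since assigning the rows of a randomly chosen Latin square still gives each agency 1/6 for every order. The 5.6% and 10% depend on the assumed six orders. The draw has also been made, and Table 2 is said to record it.

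A reader might infer that the three Aim 1 agencies are in fact unbalanced, or that the components cannot be told apart from block position. The documents support neither. The realised orders are not visible here, and lack of perfect balance is not aliasing: with position in the model, all component contrasts remain estimable in 72% of independent draws and in every draw without repeats. Short of aliasing, the cost is precision and the need for a position term. The Aim 1 parameters are deferred to the Results, so such a term may exist there.

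A reader might also carry the three-agency figures over to Aim 2. They do not apply, because Aim 2 uses six agencies. The plan already tempers its claims, allowing a functional relation to be only tentatively confirmed.

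What stands is narrower: no scheme is described that assures balance or separability in the trio, and no position term is described that would deal with imbalance.

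**Conclusion.** The point holds as a design risk and a reporting gap. On the procedure as described, and assuming that all six orders were eligible, perfect position balance in the Aim 1 trio had a probability of 5.6% (independent draws) or 10% (no repeats). Under independent draws there was a 28% chance that at least one component would share its position across all three agencies, leaving some contrasts inseparable from position. Under draws without repeats that chance is zero.

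The conclusion rests on four things: the trio being #2, #5 and #6; the full set of six orders; the absence of an undescribed joint constraint; and complete data in all three blocks of the trio. On the last, the Consultant Fidelity section says that one agency stopped after 6 of 12 sessions but does not say which. Whether any imbalance occurred has to be read from Table 2.

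**What to change.** **At the design stage.** Draw orders without replacement from the six permutations. Over six agencies this balances both position and immediate predecessor, provided that all complete; the agency that stopped at 6 of 12 sessions never reached its third block. It does not make the Aim 1 trio a Latin square (10% chance), but it keeps every component contrast in the trio estimable after adjustment for position.

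Optionally, since #5 and #6 were recruited after agencies #1 to #4 had started data collection, randomise between them the two orders that complete a Latin square with #2. That guarantees position balance in the trio. The cost is that each component then has only one possible preceding component, so first-order carry-over is tied to component.

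Either route needs only a different randomisation list, with no extra agencies or sessions. The last orders become predictable to the statistician holding the list.

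**Now that the orders are fixed.**
1. State the permutation set, whether orders could repeat, and any joint constraint.
2. Tabulate block position by component for #2, #5 and #6 from Table 2.
3. Add a block-position term as a sensitivity analysis in Aims 1 and 2. In Aim 1, the three position indicators and the three component indicators have the same sum, so one constraint is needed; the component-versus-component contrasts are what to report from this model.
4. Limit the active-ingredient claim to components whose block position differs across the three agencies.

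These steps cost a table, a few sentences and one further model per outcome.

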Skill rehearsal condition. With one week's notice, the consultant sent an email that assigned a series of role plays that corresponded to the structure of a Project ImPACT session. The assignments included the following role play scenes: Scene A: setting the session agenda, reviewing the previous session's Practice Plan (homework sheet), and introducing the new NDBI technique (e.g., Prompts for Using Communication); Scene B: introducing the video model to demonstrate the new technique, screen sharing the video model, and helping the parent to reflect on the video model; Scene C: live caregiver practice with coaching comments (i.e., a videotaped parent-child interaction was screenshared by the consultant, and the consultant paused throughout to solicit coaching comments from the clinician); and Scene D: reflecting on the parent practice section and developing a new Practice Plan (i.e., homework sheet) for between-session practice on the technique. The email also included information about which session number the group would practice (e.g., Session 14: Prompts for Using Communication), background information about the pseudo client and caregiver (e.g., child's age, language level, and intervention goals), and the necessary paperwork for the session (e.g., completed Practice Plan for homework review section of the session).

The email also outlined directions for how each clinician would take turns pretending that they were the coach (picking up where the last scene ended), with the consultant role playing as the caregiver. The consultant reminded the clinicians to refrain from providing oral feedback and to instead write any feedback comments on a worksheet provided at each consultation session. These reminders were to ensure that the research design could clearly distinguish the effects of *rehearsing* parent coaching skills used in Project ImPACT sessions (i.e., Skill Rehearsal condition) from *receiving performance feedback* (i.e., Feedback condition).

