Manual adherence. Adherence to the Project ImPACT manual content was assessed by coders naïve to session number or timepoint via the Project ImPACT Coaching Fidelity Checklist (Ingersoll & Dvortcsak, 2019) to identify the extent to which clinicians adhered to lesson plans and content from the manual. Items include appropriate use of Project ImPACT program materials (e.g., use of handouts and the parent manual), appropriate description of Project ImPACT NDBI techniques to caregivers, sufficient time spent on critical Project ImPACT session components (e.g., at least 12 minutes of caregiver practice time), and presence of parent coaching clinical skills (e.g., provision of effective positive coaching feedback). Certain items that are considered more central to a parent coaching approach are weighted heavier (e.g., sufficient caregiver practice time, providing corrective feedback to caregivers), whereas other items are weighted less (e.g., assigning reading for the next session as homework). Clinically, a score of 80% or higher on this measure is considered “at fidelity.” All Project ImPACT sessions were randomly assigned to be scored by two independent coders naïve to timepoint and condition. Coders needed to meet training criteria of 3 videos in a row with 80% of items in exact agreement with the master coder prior to coding for the actual dataset. Monthly meetings with the coding team were held in which all members independently coded a video, and the group compared their scores to the master codes and discussed discrepancies. Once trained, coders met to discuss each videotaped session and resolved any disagreements by consensus. Consensus scores were used in the final analyses.

Parent coaching competency. Competency in parent coaching was assessed by coders naïve to session number or timepoint via the Parent Empowerment and Coaching in Early Intervention (PEACE) measure (Pellecchia et al., 2023) which utilizes a 5-point Likert scale to assess quality and competency in delivering collaborative coaching techniques used in parent-

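### Masking of the fidelity coders is overstated: consultant coders could not be naïve to condition, and lesson content probably reveals baseline versus consultation to the client-session coders

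*Combined protocol and SAP*

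**What the plan says.** All references are to the combined protocol and SAP.

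- **Manual adherence.** Scores were "assessed by coders naïve to session number or timepoint via the Project ImPACT Coaching Fidelity Checklist", and the stated purpose was "to identify the extent to which clinicians adhered to lesson plans and content from the manual". Later in the same paragraph the masking is described differently: "All Project ImPACT sessions were randomly assigned to be scored by two independent coders naïve to timepoint and condition". The first statement covers session number or timepoint; the second covers timepoint and condition. One listed item is "appropriate description of Project ImPACT NDBI techniques to caregivers".
- **Baseline phase.** The coaching manual contains "lesson plans for each of the 24 sessions".
- **Skill rehearsal condition.** The role plays mirror a real session, whose opening part includes "reviewing the previous session's Practice Plan (homework sheet), and introducing the new NDBI technique". Session number is tied to a named topic, for example "Session 14: Prompts for Using Communication".
- **Parent coaching competency (PEACE).** The same two masking descriptions appear. Scoring against lesson plans is not mentioned.
- **Consultant Fidelity to Consultation Conditions.** Consultation sessions were "assessed by 2 coders naïve to condition and timepoint using the Project ImPACT Consultation Adherence Checklist". The example items differ by condition: clip introductions and praise for Feedback, role-play scenes for Skill Rehearsal, solutions to implementation challenges for Case Support. Coders also timed these activities.
- **Multilevel modeling for Aim 1.** The model estimates the change in level from baseline to each consultation condition.

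**The concern.** A coder who judges adherence to a lesson plan normally has to know which lesson is being delivered, and the recording shows it. Lessons are numbered and clinicians were asked to follow the manual weekly, so an early lesson suggests baseline and a late one suggests consultation. That is the contrast the Aim 1 model estimates. If coders expect improvement, later recordings may be scored more generously, and consensus between two coders does not remove an expectation they share. Most PEACE scores come from one primary coder on a 5-point scale, with intraclass correlations of 0.69 (Collaboration) and 0.63 (Reflection and Problem-Solving), so there is room for judgement there too.

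The consultant-fidelity scores are used to support experimental control. A reader would take the 100%, 93% and 97% figures as scored without knowledge of condition, which the checklist does not allow.

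**Working it through.** **Consultant coders.** This needs no arithmetic. A coder cannot score whether a role-play scene was finished, or time the minutes in role play, without seeing that the session is Skill Rehearsal. The same applies to clips (Feedback) and problem-solving (Case Support). Naivety to condition is ruled out by the instrument. Naivety to timepoint remains possible, because component order was randomised by agency.

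**Client-session coders: session number.** There is one plan per session, and the score concerns adherence to the plan. Sessions 1, 2 and 23 are described elsewhere in the document as different in kind. No procedure for hiding the lesson is described, and no check of masking is reported.

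**How well lesson number reveals phase.** Inputs from the document:

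- Cancellation in the three Aim 1 agencies: 76/299 = 0.254, which reproduces the stated 25.4%.
- Agency 2 baseline: randomised within 3-6 weeks. At least 3 usable weeks after dropping sessions 1 and 2 implies 5-6 weeks.
- Agencies 5 and 6: 6-9 weeks plus a 1-week extension = 7-10 weeks.
- Consultation: 12 weeks.

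Assumptions: lessons in manual order, one per held weekly session; one family per clinician from baseline week 1; independent cancellations; sessions 1 and 2 excluded. Table 2 is not legible in the text, so baseline lengths were varied over these ranges.

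Simulated classification of recordings as baseline or consultation by the best single lesson-number cut-off:

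| Scenario | Best cut-off correct | Always guessing consultation |
|---|---|---|
| 25.4% cancelled, baseline lengths drawn over the ranges | about 0.89 | 0.71 |
| 25.4% cancelled, five fixed sets of baseline lengths | 0.88-0.91 (AUC 0.94-0.97) | 0.67-0.77 |
| 25.4% cancelled, some clinicians (30-60%, assumed) add a later-starting family | about 0.83-0.85 | 0.74-0.77 |

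With one family each, accuracy was 0.914 with no cancellations and 0.862 with 40% cancelled.

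Across the five fixed sets at 25.4% cancellation, the share of recordings that are baseline was 96-99% at lesson 3, 57-83% at lesson 5, 29-67% at lesson 6 and 9-51% at lesson 7. With a baseline of at most 10 weeks and one session a week, lesson 11 or later cannot be baseline. About 99% of recordings of lesson 9 or later are consultation sessions. That figure depends on cancellations: with none and a 10-week baseline, lessons 9-10 are baseline and 11-22 consultation, so 12/14 = 86%.

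**Is one family per clinician realistic?** The Aim 1 text counts 60 models for 5 outcomes, so 60/5 = 12 clinicians. Then 299/12 = 24.9 scheduled sessions each, whereas the longest schedule is 10 + 12 = 22 weeks, and 12 × 22 = 264 < 299. Some clinicians therefore had more than one family, or phases ran longer than planned. This is why the third row of the table matters.

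**The case against.** A reader might infer that masking to timepoint was impossible and that the baseline-to-component gains are simply unmasked. The documents do not support that. Nothing says coders knew an agency's identity, baseline length, start date or component order. Baselines were staggered, recordings were randomly assigned to coders, a quarter of sessions were cancelled, and lessons 5-7 are mixed between phases. The cut-off accuracy also has to be read against the 71% obtained by always guessing consultation, and it presumes a coder who knows the best threshold. These points stand, and they limit the conclusion to probable compromise.

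A reader might also infer that the gains are inflated. Neither the direction nor the size of any bias can be derived from the documents.

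The lesson-plan argument applies directly to adherence only. The adherence items given as examples are generic, so session-specific scoring is a strong inference from the stated purpose of the measure. For PEACE, the only route is topic cues in the same recordings.

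Finally, the Aim 1 prediction is that feedback adds to the other two components, which is a between-component question, and two of the three adjacent-phase transitions in the visual analysis are between components. Lesson number alone does not reveal which component was running, because order was randomised by agency. This stands, and it is why those comparisons are largely protected. It does not rescue the model estimates, which are all changes from baseline.

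The consultant checklist is a descriptive integrity check, and the report is open about contamination: 68% of Skill Rehearsal sessions contained some feedback. That lowers the stakes but does not make the masking statement true.

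**Conclusion.** The concern holds in three graded parts. Consultant coders' naivety to condition is contradicted by their own checklist. Adherence coders' naivety to session number is not credible as described. Masking to baseline versus consultation is probably compromised and, as far as the documents show, untested: lesson number classifies phase correctly about 89% of the time against 71% by guessing, or about 83-85% against 74-77% with some later-starting families. About 99% of recordings of lesson 9 or later are consultation sessions at the stated cancellation rate. These figures are illustrative and rest on in-order weekly delivery and assumed baseline lengths. No biased result has been shown; what changes is how much protection the baseline-to-component contrasts can claim.

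**What to change.** 1. Delete the statement that consultant-fidelity coders were naïve to condition. Keep naivety to timepoint only if it was in fact withheld.
2. Reconcile the two masking statements under Manual adherence, and the matching pair under Parent coaching competency. State what was withheld from coders (timepoint, agency schedule, component order, if so) and how, that the lesson was identifiable from session content, and that masking to phase was not tested, if that is the case.
3. Claim masked assessment only for comparisons between components. Report baseline-to-component changes as possibly unmasked to phase.
4. As a supportive check, rerun the baseline-to-component adherence model on strictly timed or counted items already coded: the 12-minute caregiver-practice item and any others of that kind. Handout use does not qualify, because it is scored on whether use was appropriate, which is a judgement.

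The cost is wording plus one supportive analysis of existing item scores. The masking claim becomes weaker. The supportive outcome is narrow and may come down to a single item, so it can support the main adherence result but not replace it. It does not address PEACE.
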